#### 3.6 Description of the intervention

In this section, the intervention is descripted in details.

The experimental group (EG) use the engAGE system in two different settings: at healthcare organization and at home. At the healthcare organization, the primary end user (SMCI) interacts with Pepper. The interaction **at healthcare organization** is supervised by tertiary end users (formal caregivers, i.e., occupational therapist, psychologist, nurse, etc...) and includes the following activities: dialoguing with the robot, storytelling, drama play, cognitive and physical games. This interaction is planned to last about **1 hour and to be scheduled twice a week for 6 months**. **At his/her home**, the older user interacts with the tablet and is supervised by the relative informal caregiver. Also in this case, the user plays cognitive and physical games installed on MEMAS app. Even this activity is **performed for 0,5 hour, every day for 6 months**. Throughout the whole period of experimentation (unless (s)he decides otherwise), the older user wears the smartwatch that measures his/her physiological parameters and the steps. Any activity performed by the seniors is assigned by formal caregiver and can be personalized taking into account the user's abilities (difficulty levels of the games), lifestyle (reminding and monitoring services), and social interactions.

The activities performed by the user through the engAGE system are schematized in the figure below:

Figure 3. Summary of engAGE activities

Table 7. Games of the Engage platform

Name of games	Description
	Familiar games

Crossword	Helps with long term memory, having	★: easy level (infinite tips)			
	definition or pictures.	★★: medium level (limited tips)			
Karaoke	Helps SMCI to have fun while singing songs they already know (train memory without noticing).	★★★: hard level (no tips)			
Memory card	Helps with spatial memory, which can help SMCI to find lost objects in the future.				
Sudoku	Helps with visual memory, using numbers instead of letters can be easier and more enjoyable. It's an appreciated game for SMCI.				
2 differences game	Helps to stay focus, observe, retain the information to seek.				
Quizzes					
Picture quiz	Find the celebrities/animals behind.				
	$\star$ : picture $\star$ $\star$ : pixelated photo $\star$ $\star$ $\star$ :	★: silhouette			
Musical quiz	Seniors interviewed share a common passion for music. Musical games and quizzes should be implemented. SMCI will have to complete lyrics of famous songs, recognize singers or the name of the songs and determine some noises.				
	★: remember the singer ★ ★: remember remember both	r the song's name $\star$ $\star$ $\star$ :			
Cultural quiz	Questions regarding arts & literature, entertainment, geography, history, science & nature, and sports & leisure. SMCI will have to answer in different manners.				
	$\star$ : two options $\star$ $\star$ : four options $\star$ $\star$	: free answer			
Physical games					
Miming	The robot being able to move, it can show SMCI some moves to train their physical condition. The robot can show some videos to the senior that he/she will copy. It can also show a picture that the senior has to interpret.				
	★: reproduce robot actions ★ ★: copy actions interpret, mimics an image	ctions on video $\star \star \star$ :			
Dancing	Dancing on songs they know and like, wit	h simple dance steps.			

	★: reproduce robot steps ★ ★: learn new steps in video ★ ★ : learn new choreography				
Doing yoga	Few SMCI have balance problem which can be helped by doing some simple exercises yoga.				
	
 
★: breath exercises ★★: some relaxing exercises (meditation) ★★★:
 
balance exercises
 
				
Story / plays telling					
Story listening	SMCI have to listen to the story told by the robot and answer questions that appear during the story telling.	No difficulties levels will be set up, but scores will show the performance of the			
Plays/poems reciting	SMCI have to listen to theatre plays or songs and learn them with the robot (only short and well-known parts) "Be or not to be".	SIVICIS.			

#### 3.6.1 The control group

The control group (CG) will be given a booklet containing some suggested activities to do at home.

They will be evaluated at T0 and at T6 like the EG.

A first and a final meeting will take place in order to introduce and explain the project to the volunteers, and to show the results collected during the experimentation.

#### 3.7 Work hypothesis

#### Work hypothesis

In this section, the hypothesis is presented along with solutions to measure the impact on those aspects.

- 1. Is there any improvement in the cognitive status?
  - Comparison of MAC-Q (before and after)
    - between groups (EG Vs CG)
    - o intra-group (EG)
- 2. Is the system usable for people with MCI?
  - Analysis of SUS in the EG
  - Analysis of UTAUT in the EG
  - stratifying for MCI
- 3. Is it the system effective in supporting lifestyle of people with MCI and their carers?
  - Adherence to the system to be assessed technically:
    - $\circ \quad \text{Nr. of interactions}$
    - o Nr. planned activities respected
- 4. And the quality of life of the participants?

- Comparison of QoL and WEMBS (before and after)
  - between groups (EG Vs CG)
  - o intra-group (EG)
- For Carers: Comparison of QoL and ZARIT (before and after)
  - between groups (EG Vs CG)
  - o intra-group (EG)
  - improvement of quality of work for Formal carers (from semi structured interview)
- 5. From semi-structured interview:
  - analysis of single modules' effectiveness/perception;
  - cost-benefit analysis;
  - willingness to pay.

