#### 3.4 Outcomes

In this section the outcomes measured throughout the field trials are reported. The main focus of the engAGE project, and so of the field trial, is the perceived stability of cognitive capabilities of people with MCI. In second place, the acceptance and the usability of the platform, as well as the caregivers' benefits have to be assessed. Thus, the outcomes are the following:

- PRIMARY END USERS (SMCI):
  - Primary outcome: perceived stability of cognitive status (MAC-Q)

- Secondary outcomes: Adherence to intervention, wellbeing, quality of life, acceptance and usability, cost-benefit analysis
- SECONDARY END USERS (INFORMAL CAREGIVERS):
  - Reduction/stability of informal caregiver's burden
  - Improvement of well-being, psychological status
  - Acceptability, usability and affordability of the solution
- TERTIARY END USERS (FORMAL CAREGIVERS):
  - Improving quality of work.

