#### 3.5 Scales and tools

In this section the questionnaires/scales asked to the end users are presented in the following tables, by indicating also at which time of the intervention a questionnaire/scale is asked.

Table 5. Questionnaires and scales asked to the senior with MCI during the field trial

PROTOCOL of QUESTIONNAIRES for SMCI	R	то	Т1	Т2
Socio-demographics checklist*		х		
Montreal Cognitive Assessment (MoCA) [IT - SW]	Х			х
Reisberg Scale	Х			
4-items Geriatric Depression Scale (GDS)	х			
Clinical Frailty Scale	х			
Memory Assessment Clinics – Questionnaire (MAC-Q)	х			х
Adherence to the system use (to be collected technically)			х	х
UCLA loneliness scale (social connectedness)		х		х
Warwick-Edinburgh Mental Wellbeing Scale (WEMWBS)		х		х
EQ-5D-5L (VAS)		х		х
Unified theory of acceptance and use of technology (UTAUT)			х	х
Quality of Life–Alzheimer's Disease (QoL-AD)		Х		х
System Usability Scale (SUS)			х	х

Semi-structured interview on acceptance, usability, willingness to pay		х	х	
--	--	---	---	--

PROTOCOL of QUESTIONNAIRES for IC/FC	R	то	Т2
Socio-demographics checklist	Х		
Zarit Burden Interview		х	Х
Adherence to the system use (to be collected technically)			х
UCLA loneliness scale (social connectedness)		х	х
Warwick-Edinburgh Mental Wellbeing Scale (WEMWBS)		х	х
EQ-5D-5L		х	Х
System Usability Scale (SUS)			Х
Semi-structured interview on acceptance, usability, willingness to pay, quality of work			х

Table 6. Questionnaires and scales for formal and informal caregivers

The quantitative tools are all standardized, and they are:

The **Montreal Cognitive Assessment (MoCA)** [1] is a widely used screening assessment for detecting cognitive impairment. The MoCA is a one-page 30-point test administered in approximately 10 minutes. The test and administration instructions are available for clinicians online. The test is available in 46 languages. The MoCA assesses several cognitive domains: the short-term memory recall task (5 points), visuospatial abilities (4 points), alternation task (1 point), verbal abstraction task (1 point), attention, concentration, and working memory (6 points), language (6 points), abstract reasoning (2 points), and orientation to time and place (6 points).

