The **Reisberg Scale** [2] consists of 7 major clinical stages. It is used by clinicians and in care settings, but may be especially helpful for caregivers, as it is noticeably detailed regarding the general abilities of an individual at each stage and provides information about what to expect at different stages. The scores go from no cognitive decline (1) to very severe cognitive decline (7), through stages 2, 3, and 4 that are respectively: Very mild cognitive decline (age-associated memory impairment), mild cognitive impairment, and moderate cognitive decline.

The **4-items Geriatric Depression Scale (GDS)** [3] is a 4-items scale whose answers are yes or no. If all the items are answered negatively then the depression is excluded; if only one item is answered positively then the situation is uncertain; if at least 2 items are answered positively, the patient is depressed. Thus, this scale is easy and quick, and very useful in excluding depression.

The **Memory Assessment Clinics – Questionnaire (MAC-Q)** [4] is a 6-item scale that uses a 5-item Likert scale from "much better now"=1 to "much worse now"=5, and the last question scores double. The questionnaire asks the person to compare his or her memory with a previous period to measure age-related memory decline. Five items address specific situations frequently reported as problematic by those who experience memory loss with age. One item is a global item assessing general memory decline. A cutoff of 25 points or more indicates that the individual has a memory disorder.

**Clinical Frailty Scale (CFS).** [5] This descriptive scale divides the older participants into 9 classes based on the information provided by them and their relatives: between 1 and 3 the patient is non-frail, pre-frail if 4, he is frail from 5 to 9.

The **UCLA scale** [10] is a 20-item scale designed to measure one's subjective feelings of loneliness as well as feelings of social isolation. Participants rate each item as either O ("I often feel this way"), S ("I sometimes feel this way"), R ("I rarely feel this way"), N ("I never feel this way").

**EQ Visual Analogue Scale (EQ VAS)** [11] records the respondent's self-rated health on a 20 cm vertical, visual analogue scale with end-points labelled 'the best health you can imagine' and 'the worst health you can imagine'. This information can be used as a quantitative measure of health as judged by the individual respondents.

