## 4 Data Management

#### 4.1 Statistical Analysis

The first step of the data analysis will deal with the description of the sample. Continuous variables will be reported as either mean and standard deviation or median and interquartile range on the basis of their distribution (assessed using Kolmogorov-Smirnov test). Categorical variables will be expressed as an absolute number and percentage. Mann-Whitney U tests (for non-normal distribution), or Chi-Square tests (normal or non-normal) will be used to compare the independent and dependent variables between the pre- and post- conditions, in addition to simple descriptive statistics (means, medians and SDs as appropriate).

In order to verify the achievement of the primary endpoint (i.e., MAC-Q), subscales of the questionnaire will be calculated. Means and standard deviation or medians and iqr of the scores will be reported according to their distribution. Correlation coefficients (Pearson for normally distributed variables, Spearman for non-normally distributed variables) of the sub-scales with the other rating scales at each stage of the study and with the main characteristics of the subjects will be calculated to check for potential determinants of higher acceptability.

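### The only 'before' MAC-Q is the recruitment score that had to be 25 or more for entry, so regression to the mean biases the within-EG before-after comparison towards improvement or apparent stability

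*Combined protocol and SAP*

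**What the plan says.** - **Outcome.** Section 3.4 names the "Primary outcome: perceived stability of cognitive status (MAC-Q").
- **Scale.** Section 3.5 scores the items "from 'much better now'=1 to 'much worse now'=5, and the last question scores double". Higher is therefore worse, and a fall reads as improvement. The same section adds: "A cutoff of 25 points or more indicates that the individual has a memory disorder".
- **Entry.** Section 3.2.4 admits seniors only with MAC-Q of 25 or more, which is the impaired side of that cutoff.
- **Timing.** In Table 5 (section 3.5) the row "Memory Assessment Clinics – Questionnaire (MAC-Q") is marked at R and T2 only. Annex 3 agrees: the form is in the recruitment and T2 packs and not among the T0 forms. Section 3.6.1 says that controls are evaluated at T0, but no MAC-Q is scheduled there for either arm.
- **Hypothesis 1.** Section 3.7 asks "Is there any improvement in the cognitive status" and answers it with "Comparison of MAC-Q (before and after"), first EG against CG and then "intra-group (EG"). It does not say which of the two decides.
- **Analysis.** Section 4.1 says that Mann-Whitney U or chi-square tests "will be used to compare the independent and dependent variables between the pre- and post- conditions". It gives no paired test, no baseline adjustment and no separate between-group analysis of change.

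**The concern.** A person whose score varies from one occasion to the next is more likely to be admitted on a day when it is high. When a group is chosen because one reading reached a threshold, its mean at the next reading moves back towards the mean of the pool it came from. Here the threshold is on the worse side, so that movement looks like improvement. Because no MAC-Q is taken between recruitment and T2, the whole of the movement falls inside the before-after difference.

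The EG-only comparison cannot separate this from an effect of the platform. It can show improvement where there is none. It can also cancel a true decline, so that EG appears stable, and perceived stability is exactly what section 3.4 names as the primary outcome. Section 3.7 sets the EG-only comparison beside the randomised one without ranking them, so a report could rest on it even if EG and CG do not differ.

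**Working it through.** The plan gives no alpha, power, effect size, SD or MAC-Q reliability, so it has no figure of its own to reproduce.

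**Inputs from the documents**
- Score range: lowest 5×1 + 2 = 7, highest 5×5 + 10 = 35.
- Selection: MAC-Q of 25 or more; 24.5 serves as the continuity-corrected cutoff for whole-number scores.
- EG size, summing the site ranges in Table 2: 20+20+8 = 48 to 22+23+10 = 55; n = 50 is used. CG: at least 30.

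**Assumed inputs (not in the documents)**
- MAC-Q in the screened pool before selection: mean 23–27, SD 3.5–4.5.
- Correlation r between the recruitment and T2 readings: 0.6–0.9.
- No true change; two-sided 0.05, hence 2.5% in the direction of improvement.

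**Expected fall with no effect**

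fall = (1 − r) × SD × φ(a) / (1 − Φ(a)), with a = (24.5 − mean) / SD

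- Mean 25, SD 4.5, r 0.7: a = −0.5/4.5 = −0.111; φ/(1−Φ) = 0.3965/0.5442 = 0.729; fall = 0.3 × 4.5 × 0.729 = 0.98.
- Mean 23, SD 4.5, r 0.6: a = 0.333; 0.3774/0.3694 = 1.021; fall = 0.4 × 4.5 × 1.021 = 1.84.
- Mean 23, SD 3.5, r 0.6: a = 0.429; 0.3639/0.3341 = 1.089; fall = 0.4 × 3.5 × 1.089 = 1.52.
- Mean 27, SD 3.5, r 0.9: a = −0.714; 0.3091/0.7625 = 0.405; fall = 0.1 × 3.5 × 0.405 = 0.14.

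Simulation with scores rounded and clipped to 7–35 gives 0.99, 1.85, 1.56 and 0.15, in agreement.

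**How often EG alone (n = 50) shows a significant false improvement**

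| Mean, SD, r | Paired test | Unpaired Mann-Whitney (4.1) |
|---|---|---|
| 23, 3.5, 0.6 | about 96% | about 86–87% |
| 25, 4.5, 0.7 | about 56% | about 21% |
| 27, 3.5, 0.9 | about 10% | about 0% |

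Repeat simulations move these by a few percentage points (for the middle row, 55–56% and 18–21%). The Mann-Whitney test flags the artefact less often because it ignores the pairing; the mean fall is the same.

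**Wider inputs.** With mean 23–29, SD 3–5 and r 0.5–0.85, the fall runs from 0.06 to 2.5 points, and false improvement is 4–97% by paired Wilcoxon and 0–92% by Mann-Whitney.

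**EG against CG.** In the same wider simulations (50 against 30, no effect), a between-group test of change rejected in about 4–6.5% of trials, close to the nominal 5%.

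**With a true decline.** At mean 25, SD 4 and r 0.8 the artefact is 0.2 × 4 × 0.720 = 0.58 points. A true worsening of 0.5 points then leaves an apparent fall of about 0.1, and a paired test reports improvement in about 4.5% of trials. The false positive is masked, but a group that got worse appears stable.

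**The case against.** The strongest reply is that the design already contains the protection. Subjects are randomised after meeting the criteria, both arms pass the same threshold, and section 3.7 lists EG against CG first. That stands. A reader might infer that the whole primary analysis is biased; the documents do not support this, and the between-group simulation contradicts it. Nor does section 3.7 say that the EG-only result may stand alone as proof. The point is only that nothing prevents it, and that no CG before-after change is set beside it.

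The size is also open to challenge. Every distributional input is assumed. Recruitment through neurology units, a memory centre and an Alzheimer day-care centre may give a pool already well above 25, where truncation is mild: at mean 27, SD 4 and r 0.8 the fall is about 0.37 points, and Mann-Whitney flags it in about 1% of trials. The paired rates also assume a test that section 4.1 does not name. Both objections limit the magnitude, not the direction.

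Finally, section 3.1 calls the trial a pilot concerned mainly with usefulness and usability, with only a partial evaluation of effectiveness, and sets no alpha or decision rule. That lowers the stakes. But the same section lists effectiveness against cognitive decline as a goal, and MAC-Q is the primary outcome, so the comparison will be read as evidence on it.

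**Conclusion.** The point holds for the intra-group comparison. As planned, the EG before-after change in MAC-Q is biased towards improvement, or towards stability that hides decline, because its baseline is the selecting score. The EG-CG comparison is unaffected.

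Under the main assumptions (screened mean 23–27, SD 3.5–4.5, r 0.6–0.9) the bias is about 0.15–1.85 points on the 7–35 scale. False improvement at n = 50 is about 10–96% with a paired test and about 0–87% with the Mann-Whitney test in section 4.1, against 2.5%. The middle case gives about 1 point, 56% and 21%.

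It would be tempting to say that EG will show a significant improvement whatever the platform does. The documents do not support that: they give none of the quantities that fix the size, the effect is near zero if MAC-Q is very stable or most people screened score well above 25, and true decline could mask it. Only the expected direction is certain, given imperfect retest correlation.

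**What to change.** 1. **Text, section 3.7.** Make the EG-CG difference in MAC-Q the only test of hypothesis 1. Label the EG before-after change descriptive, show it beside the CG change, and draw no claim of improvement or stability from it. This costs a few lines and by itself removes the inferential problem.
2. **Data, Table 5 and the Annex 3 T0 pack.** Also collect MAC-Q at T0 in both groups, before the allocation is disclosed, and use it as the baseline; keep the recruitment score for eligibility only. This costs one six-item form at a visit that already takes place. It reduces the regression but may not remove all of it: the interval between recruitment and T0 is not stated, and if the errors at the two readings are correlated, part of the selection effect carries over. It therefore supplements the first change and does not replace it.

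### Hypothesis 4 ranks the uncontrolled before-after change in the experimental group equally with the randomised comparison, so the chance of a false claim of quality-of-life benefit is not controlled

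*Combined protocol and SAP*

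**What the plan says.** Section 3.7 of the combined protocol and SAP poses hypothesis 4 as an open question about participants' quality of life. It names two comparisons for seniors, "Comparison of QoL and WEMBS (before and after", and two for carers, "For Carers: Comparison of QoL and ZARIT (before and after". Under each it lists "between groups (EG Vs CG" and "intra-group (EG" at the same bullet level. A further item, "improvement of quality of work for Formal carers (from semi structured interview", has no numerical criterion.

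Section 3.4 sets one level of ranking. MAC-Q is primary, and quality of life and wellbeing appear under "Secondary outcomes: Adherence to intervention, wellbeing, quality of life, acceptance and usability, cost-benefit analysis".

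In section 3.5, Table 5 schedules "Quality of Life–Alzheimer's Disease (QoL-AD", WEMWBS and EQ-5D-5L (VAS) for seniors at T0 and T2. Table 6 schedules EQ-5D-5L for carers but not QoL-AD.

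Section 4.1 says its tests "will be used to compare the independent and dependent variables between the pre- and post- conditions". It names no EG-versus-CG test, significance level, multiplicity rule or deciding contrast.

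**The concern.** The two contrasts answer different questions. The change within the EG contains any effect of the system plus whatever else moves scores over six months: attention, expectation, season, answering the same questionnaire again. The EG-versus-CG difference removes whatever both arms share. Shared influences are plausible here, because the controls also receive an activity booklet and meetings (section 3.6.1), and section 5.1 gives all end users, controls included, access to the researcher.

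As the plan stands, an analyst who follows section 4.1 literally would produce the before-after result, and section 3.7 would let it stand beside the randomised result as evidence. The two can disagree, and no rule says which one is believed. Having several scales adds further chances of a favourable finding. At stake is a published statement that the system improves quality of life when the trial's own control group shows the same change.

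**Working it through.** The plan gives no significance level, SD, effect size or error rate for this hypothesis, so there is no figure of its own to reproduce.

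**Inputs from the documents**
- Named scales: 2 for seniors and 2 for carers. Contrasts: 2. That gives 2 × 2 = 4 senior tests and 4 × 2 = 8 tests in all.
- Group sizes (Table 2): EG from 20 + 20 + 8 = 48 to 22 + 23 + 10 = 55; CG at least 30. The total is 78 to 85, which covers the 80 in section 3.1. I use EG 50 and CG 30.

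**Assumptions**
- Two-sided 5% per test, so 2.5% in the direction of benefit.
- t-tests on change scores (section 4.1 does not name these).
- Correlation between scales of 0 to 0.7.

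**Step 1: no change in either arm.** On one scale the two test statistics share the EG data, and their correlation is √[(1/50) / (1/50 + 1/30)] = 0.61. If all tests were independent, the chance of at least one false benefit would be 1 − 0.975⁴ = 9.6% for four tests and 1 − 0.975⁸ = 18.3% for eight. Simulation with the actual dependence gives:

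| Tests | False benefit | Any significant result |
|---|---|---|
| 2 senior scales × 2 contrasts | about 7-9% | about 14-17% |
| 4 scales × 2 contrasts | about 11-17% | about 22-30% |
| 1 scale, EG versus CG only | 2.5% | 5% |

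Simulation error is under one point: with 6,000 runs, 2 × √(0.16 × 0.84 / 6000) = 0.9 points.

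The four-scale row supposes carers in both arms. If there are no control-group carers, the carers contribute only two EG-only tests (4.5% for at least one false benefit at correlation 0.5). Combined with the senior figure of 7.8%, and taking carers as independent of seniors, the total is 1 − (1 − 0.078)(1 − 0.045) = 12%.

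**Step 2: both arms change equally, with no effect of the system.** Let d be the shared change in units of the SD of change. The EG-only test is favourable with probability 1 − F(2.01; 49 df, noncentrality d√50), where F is the noncentral t distribution.

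| d | d√50 | EG-only, one scale | EG versus CG, one scale |
|---|---|---|---|
| 0.1 | 0.71 | 10% | about 2.5% |
| 0.2 | 1.41 | 28% | about 2.5% |
| 0.3 | 2.12 | 55% | about 2.5% |
| −0.1 | −0.71 | 0.4% | about 2.5% |

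At d = 0.3, EG sizes of 48 to 55 give 53-59%. With two scales correlated at 0.5, at least one EG-only test is favourable 42% of the time at d = 0.2 and 72% at d = 0.3.

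**Step 3: the two sources of error compared.** Multiplicity alone raises the rate from 2.5% to somewhere between 7% and 17%. Shared improvement can raise it far more, and only through the EG-only contrast. The choice of contrast therefore matters more than the number of scales.

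**The case against.** The best defence has four parts.

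1. **Quality of life is secondary in a self-described pilot.** This stands, and it lowers the priority. The effectiveness goal in section 3.1 concerns cognitive decline, so it cannot be used to argue that hypothesis 4 is confirmatory. But the plan does not call hypothesis 4 exploratory either, and section 3.7 sets out comparisons for it.
2. **No decision rule is stated, so none is wrong.** A reader might infer that any single favourable test, including an EG-only one, counts as a yes. The documents do not say that; they leave the matter open. What stands is the absence of a rule, together with a section 4.1 that describes only the weaker contrast.
3. **No drift is given.** This also stands. The larger percentages depend on an improvement in both arms that the documents neither state nor exclude. A shared decline would make the EG-only test work against a claim.
4. **The test count can be overstated.** QoL for seniors most naturally means QoL-AD, the only scheduled scale with that name, so counting the EQ VAS as a third scale is the less natural reading. Table 2 lists informal carers in the same numbers as EG seniors and none for the CG, so the carer EG-versus-CG contrast may have no comparator. I therefore do not rest the point on the count of eight.

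**Conclusion.** The point holds as a weakness in the choice of contrast. Section 3.7 gives an uncontrolled before-after change equal rank with the randomised comparison, section 4.1 names only the former type, and the probability of a false claim of benefit is left uncontrolled.

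Its size under the stated assumptions is several times the 2.5% of a single randomised test even without drift. It passes one half for a single EG-only test only when both arms improve by about 0.3 SD of change. A reader might infer that a false claim of benefit is likely, or that the EG-only contrast will usually show one. The documents do not support that: multiplicity alone stays well below one half, and the high figures need a shared improvement whose size and direction are unknown.

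**What to change.** In sections 3.7 and 4.1:

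- State that wherever both contrasts are listed, including MAC-Q under hypothesis 1, the effect is judged only from the randomised EG-versus-CG difference at T2, adjusted for the baseline value (for MAC-Q this is the recruitment value, since Table 5 does not schedule it at T0). Add this analysis to section 4.1.
- Report EG-only changes as descriptive, with estimates and 95% confidence intervals.
- State that QoL for seniors means QoL-AD.
- Label hypothesis 4 as secondary or exploratory. If a formal claim is wanted, adjust across QoL-AD and WEMWBS, for example by Holm. This is optional: without adjustment, the two randomised senior tests together carry about 4-5% for a false benefit.
- Report carer results as descriptive, since Table 2 lists no control-group carers.

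The cost is a few sentences. No new data are needed, because section 3.6.1 already has the controls evaluated at the start and the end like the EG. The downside is that EG-only changes can no longer be claimed as benefit. If Holm is used, there is also a small loss of power, because its first step is at 2.5%.
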